NCT03055260

Low Intensity Blood Flow Restriction Training Study

PI: [name]

Document Date: 2/1/2017

Effect of low intensity blood flow restriction training on lower extremity strength and hypertrophy

[name], DPT – Fairview/Institute for Athletic Medicine

Protocol v3.0 – February 1, 2017

Project Summary

This study is looking at the effect of blood flow restriction in the leg on overall strength gain and muscle increase. Subjects will complete baseline testing that will measure quadriceps muscle cross-sectional area via ultrasound technology, as well as complete 6 weeks of sessions (2 times per week) in which they perform controlled exercises, one leg at a time.

Subjects will be assigned to one of two groups: either the 1.) experimental group or 2.) control group. The experimental group will exercise with a blood flow restriction cuff around their right leg inflated to 100-250 mmHg (depending on participant size), and the control group will also exercise with a cuff on their right leg but with a pressure much less than that of the experimental group. Both groups however will complete the exact same protocol throughout the entirety of the study. Once the 6 weeks of training is up, muscle cross sectional area via ultrasound and 1RM will be re-tested and compared to the initial measurements.

Background

Physically active individuals with the goal of increasing muscle mass and enhancing performance often turn to resistance training. Per the American College of Sports Medicine's recommendations, 70% of a person's 1 repetition maximum, for 6-12 repetitions, is required to induce hypertrophy in human skeletal muscle. Muscle loading below this 70% 1RM has shown to be less effective for muscle hypertrophy. Recent research over the past 5-10 years has shown that low load resistance training (30% of 1RM) combined with moderate blood flow restriction has resulted in muscle hypertrophy gains similar to the traditional high load training. Blood flow restriction consists of using blood pressure-like cuffs at the proximal portion of arms or legs with the purpose of restricting ~80% of arterial flow to the muscle and 100% of the venous return. This short-term (~5 minutes for entire protocol) decrease in blood flow has been theorized to work via increased: acute muscle cellular swelling, metabolic accumulation resulting in increased muscle fiber recruitment, growth hormone release, proliferation for myogenic stem cells, and enhanced signaling of protein synthesis. BFR has shown favorable results across populations, including elderly, trained athletes, and those recovering from injury who are not able to load their joints at 70% of their 1RM. It is currently being used in rehabilitation settings as well as in professional sports.

Study Purpose/Objective

The purpose of this study is to investigate whether the addition of blood flow restriction to low load exercise, will result in changes in quadriceps hypertrophy or lower extremity strength.

Inclusion Criteria

Male or female ages 18-49

Exclusion Criteria

Pregnant, hypertensive, recent back or lower extremity injury, history of blood clotting, varicose veins, adults lacking the capacity to consent for themselves

Methods and Procedures

Session 1: baseline testing

- 5-minute warm-up; 1RM calculation for both right and left legs using a supine leg press machine; cross-sectional measurement of both right and left quadriceps muscle using ultrasound technology.
- After day 1 testing; randomly allocate subjects to either control group or experimental group

Sessions 2-9: 6 weeks of exercise protocol, 2x/week

Both the experimental and control groups will complete the same protocol for the entirety of the study:

- 5- minute warm up
- Using a single-leg press exercise machine: Subjects complete the testing protocol with either blood flow restriction (cuff inflated to 100-250 mmhg depending on size of person) or no blood flow restriction (placebo inflation) on right limb.
 - Protocol: 30 repetitions – 15 repetitions – 15 repetitions – 15 repetitions with each set separated by ~30 seconds.
 - Right and left legs will be alternating, but only right leg will have the occlusion cuff

Session 10: Re-test

- Re check 1RM, cross sectional area of quadriceps with ultrasound

Data Safety and Monitoring Plan

The PI will be responsible for monitoring and handling any potential problems that arise, including, but not limited to, informing the IRB immediately of any safety issues or concerns.

Injury

In the event that this research activity results in an injury, treatment will be available, including first aid, emergency treatment and follow-up care as needed. Care for such injuries will be billed in the ordinary manner to you or your insurance company. If you think that you have suffered a

research related injury, let the study administrators know right away. If serious injury were to occur, the PI will see to it that immediate medical attention is provided, including having the PI transport the subject to the nearest appropriate medical facility and/or contacting the appropriate emergency services.

Statistical Analyses

Independent Samples t-tests, Paired samples t-test, repeated measures ANOVAs and two-way ANOVAs will all be employed to determine difference within and between groups, across trials and conditions. SPSS v23 will be utilized for all statistical analyses.

Data and Record Keeping

The PI will be responsible for collecting and maintaining all data, and storing said data on a password-protected computer that will remain locked in a Fairview clinic office.

References

Loenneke, J. P., Wilson, J. M., Marín, P. J., Zourdos, M. C., & Bemben, M. G. (2011). Low intensity blood flow restriction training: A meta-analysis. *European Journal of Applied Physiology*, *112*(5), 1849-1859. doi:10.1007/s00421-011-2167-x

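### The protocol does not say who scans or reads quadriceps CSA at Session 10, or that this person is unaware of group, so group-aware measurement is permitted

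*Combined protocol and SAP*

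**What the plan says.** - **Session 1 (Methods and Procedures).** Baseline includes "cross-sectional measurement of both right and left quadriceps muscle using ultrasound technology". Allocation comes later: "After day 1 testing; randomly allocate subjects to either control group or experimental group".
- **Sessions 2-9.** Both groups wear a cuff on the right leg. Controls receive "no blood flow restriction (placebo inflation) on right limb". The Project Summary describes the control cuff as inflated "with a pressure much less than that of the experimental group".
- **Session 10.** The whole instruction is "Re check 1RM, cross sectional area of quadriceps with ultrasound".
- **Data and Record Keeping.** "The PI will be responsible for collecting and maintaining all data".
- **Statistical Analyses.** "Independent Samples t-tests, Paired samples t-test, repeated measures ANOVAs and two-way ANOVAs will all be employed", for comparisons within and between groups. No contrast is named as the main one.

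No section says who scans, who reads, whether either person knows the group, or whether images are stored, coded or read in batch.

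**The concern.** Measuring CSA on ultrasound involves judgement: where the probe sits, which frame is kept, where the muscle border is drawn. Someone who knows which participants trained under restriction can, without intending to, settle those judgements in the expected direction.

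The baseline scan is protected because allocation follows it; the Session 10 scan is not. A group-related shift at Session 10 therefore passes in full into the between-group difference in CSA change. A larger sample does not shrink such a shift; it makes a false positive more likely. If group-aware readings are the only record, no later analysis can separate the shift from a treatment effect. Hypertrophy is half of the stated objective.

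**Working it through.** **Step 1. Who could know the group at Session 10?**

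- Whoever sets the cuff pressure knows it, because the control pressure is much lower.
- A measurer who did not set the pressure may not know it. Both groups wear the cuff on the same leg, so neither the cuff nor the leg reveals group.
- The documents do not say which of these the measurer is.

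**Step 2. Which comparison can be biased?** Knowing only which leg was cuffed, or only the time point, produces shifts that are equal in the two groups. Those affect within-person contrasts (right versus left, before versus after) and cancel between groups. The between-group CSA comparison is biased only by a shift that depends on group.

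**Step 3. How much could it matter?** The plan gives no sample size, SD, correlation or significance level, so there is no figure to reproduce. All inputs here are assumptions:

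- n = 20 per group, no true effect, two-sided 5% test
- shift b = 0.2 SD of CSA, in the experimental right leg at Session 10
- pre-post correlation r from 0.5 to 0.95

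In units of the SD of CSA, the SD of change is √(2(1−r)). The standard error of the between-group difference in change is SE = √(4(1−r)/n). The false-positive rate is the rejection probability of a noncentral t with 2n−2 = 38 degrees of freedom and noncentrality b/SE. With two groups and two time points, the group-by-time F from a repeated measures ANOVA is the square of this t, so the same rates apply to it.

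| r | SE | b/SE | False-positive rate |
|---|---|---|---|
| 0.5 | 0.316 | 0.63 | 9% |
| 0.7 | 0.245 | 0.82 | 13% |
| 0.8 | 0.200 | 1.00 | 16% |
| 0.9 | 0.141 | 1.41 | 28% |
| 0.95 | 0.100 | 2.00 | 50% |

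For example, at r = 0.8: SE = √(4 × 0.2/20) = 0.200, b/SE = 0.2/0.200 = 1.00, rate 16.4%.

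Other inputs at r = 0.8: a 0.1 SD shift gives 8% with 20 per group and 6% with 10 per group; a 0.2 SD shift with 10 per group gives 10%.

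**Step 4. Would the untreated leg rescue the comparison?** Suppose right-minus-left change were compared between groups. A shift common to both legs of the experimental group would cancel, and the rate would return to 5%. A shift confined to the experimental right leg would not. With c the right-left correlation of change (assumed), SE = √(4(1−r)/n) × √(2(1−c)). At r = 0.8, n = 20 and b = 0.2, the rate is 11%, 13%, 16% and 24% for c = 0, 0.3, 0.5 and 0.7. The plan does not commit to this contrast in any case.

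**The case against.** The strongest reply is that this is silence, not a stated flaw. A reader might infer from the record-keeping sentence that the PI sets the cuff, scans and reads, so that CSA is known to be measured unmasked. The documents do not support that. The sentence assigns responsibility for data; it does not say who performs any of these tasks. Bias also needs a chain of unstated facts: the measurer knows the group, and that knowledge moves the reading. The placebo inflation may already keep a measurer who did not set the pressure unaware. This stands, and it limits the point to what the plan permits.

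A reader might also take 16% as the expected error rate. It is not. It is one assumed case in a range of 9% to 50%, and nothing in the documents favours any value of r, n or b. The figures show that a modest shift can matter, not that one exists.

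Three objections to the remedy also stand:

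- Coded batch reading masks the reading only. Probe placement and frame choice at acquisition remain exposed.
- Reading everything at the end moves baseline reading to after allocation, so its present protection would rest on the coding. This is most serious if the PI is the only reader.
- Staffing is uncertain. The Injury section tells participants to "let the study administrators know right away", which hints at staff besides the PI but does not establish that anyone is available.

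What the reply does not remove is that the plan gives no safeguard for a reader who does know the group, although a more protective procedure can be written down.

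**Conclusion.** The point holds as a design weakness that should be corrected. The plan names no scanner or reader, states no masking and makes the PI responsible for collecting all data, so group-aware CSA measurement at Session 10 is possible under the protocol as written. Whether it occurs, and how large any bias would be, cannot be determined from the documents.

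The size depends wholly on the assumed inputs: a false-positive rate close to nominal if the shift is small (8% at 0.1 SD, r = 0.8, 20 per group), and well above it if the shift is 0.2 SD and repeat measurements are highly correlated. The case for change does not rest on a particular rate. It rests on there being a less bias-prone way to read the images that adds no visit, no procedure for participants and no extra reader, provided that images can be stored.

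**What to change.** Add one paragraph to Methods and Procedures:

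1. Name who scans and who reads.
2. Store all Session 1 and Session 10 images without labels, under random codes that hide participant, group, leg and date.
3. After the last retest, one existing reader measures all images in random order. The CSA file is locked before the codes are linked. Existing staff who do not read images hold the key.
4. Where existing staffing allows, the Session 10 scan is done by a team member who did not set the cuff pressure and does not know the group. Otherwise, report unmasked acquisition as a limitation.
5. If the PI is the only reader, read and lock the Session 1 CSA values before allocation and do not show them at retest. Read the coded Session 10 images in random order, and report the weaker masking.

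**Cost.** One paragraph, a coding step and a delayed read. Images must be storable, which the protocol does not mention, and CSA values arrive later. Under item 3, baseline reading falls after allocation and relies on the coding. Acquisition bias is not removed by batch reading. The 1RM retest, in the same Session 10 line, has the same gap, and batch reading does nothing for it.

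### No session includes a standard harms question, so symptoms that participants do not see as a study-caused injury risk being missed

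*Combined protocol and SAP*

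**What the plan says.** Two sections of the combined protocol and SAP deal with harms.

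- **Data Safety and Monitoring Plan:** this section states a general duty: "The PI will be responsible for monitoring and handling any potential problems that arise, including, but not limited to, informing the IRB immediately" (the notice to the IRB concerns safety matters). It gives no method, timing, symptom list or form.
- **Injury:** this section covers treatment, billing and emergency response. For participants who think the research has injured them it says: "research related injury, let the study administrators know right away".

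Methods and Procedures lists what happens at each contact. Session 1 has a warm-up, 1RM testing, "cross-sectional measurement of both right and left quadriceps muscle using ultrasound technology" and then allocation. The training block is headed "Sessions 2-9: 6 weeks of exercise protocol, 2x/week" and consists of a warm-up and the leg-press sets. Session 10 is "Re check 1RM, cross sectional area of quadriceps with ultrasound".

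On exposure, the Project Summary has the experimental group exercise with a "blood flow restriction cuff around their right leg inflated to 100-250 mmHg", while controls wear a cuff "with a pressure much less than that of the experimental group". Background gives the aim as restricting about 80% of arterial flow and all venous return. The Exclusion Criteria rule out, among others, people with hypertension, past clotting, varicose veins or a recent back or leg injury. Statistical Analyses lists t-tests and ANOVAs and names no safety outcome.

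**The concern.** The exclusions show that the protocol recognises vascular and injury hazards at entry. After enrolment, no scheduled step looks for them.

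The one reporting route described in any detail filters twice. The participant must regard the problem as an injury, and must attribute it to the research. Pain, swelling, numbness or bruising that fails either test has no defined way into the data. Attribution is hard in this trial because each leg does 30 + 15 + 15 + 15 = 75 leg-press repetitions per session, so a participant could reasonably put a leg symptom down to training.

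Two things are at stake. One is safety: a symptom nobody asks about may still be unknown to the study when the cuff is next inflated. The other is the record: a harm that was never collected cannot be recovered at analysis, and a withdrawal because of symptoms would look like any other withdrawal. If the trial report later says anything about tolerability by group, it will rest on whatever happened to be volunteered or noticed.

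**Working it through.** The plan states no sample size, adverse event rate or reporting rate, so it has no figure to reproduce. The check is a reading of every listed contact, followed by an illustration under stated assumptions.

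**1. Contacts against harms items**

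| Contact | Listed content | Harms question or form |
|---|---|---|
| Session 1 | Warm-up, 1RM both legs, ultrasound both legs, allocation | None |
| Training sessions | Warm-up, leg-press sets with cuff on right leg | None |
| Session 10 | 1RM, ultrasound | None |

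The document also gives no adverse event definition, staff assessment of relatedness, collection period, rule for recording why sessions were missed, or harms table.

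**2. Under-detection (illustration)**

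Let p be the true risk of a symptom per participant, s the probability that a case is recorded, and n the number per arm. All three are assumed. The recorded risk is p × s, and the probability that an arm records at least one case is 1 − (1 − p × s)^n.

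| n | p | s = 0.2 | s = 0.5 | s = 0.9 |
|---|---|---|---|---|
| 10 | 0.1 | 0.18 | 0.40 | 0.61 |
| 20 | 0.1 | 0.33 | 0.64 | 0.85 |
| 30 | 0.1 | 0.46 | 0.79 | 0.94 |
| 20 | 0.3 | 0.71 | 0.96 | 1.00 |

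For example, with n = 20, p = 0.1 and s = 0.2: 1 − (1 − 0.02)^20 = 0.33. In that case 20 × 0.1 = 2 true cases are expected in the arm and 2 × 0.2 = 0.4 are recorded. Under-detection needs only a low s; it does not need the arms to differ.

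**3. Comparison between arms (illustration)**

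The recorded risk ratio is (p1 × s1) / (p2 × s2), with arm 1 experimental and arm 2 control.

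| True risks | s1 v s2 | Recorded ratio |
|---|---|---|
| Equal (true ratio 1.0) | equal | 1.0 |
| Equal | 0.5 v 0.2 | 2.5 |
| Equal | 0.2 v 0.5 | 0.4 |
| 0.3 v 0.1 (true ratio 3.0) | equal | 3.0 |
| 0.3 v 0.1 | 0.5 v 0.2 | 7.5 |
| 0.3 v 0.1 | 0.2 v 0.5 | 1.2 |

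Equal reporting, however low, leaves the ratio intact. Unequal reporting can inflate it, shrink it or reverse it.

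**4. Number of collection points**

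The session labels give 9 − 2 + 1 = 8 training sessions; the stated frequency gives 6 × 2 = 12. Adding the re-test, that is 9 or 13 points at which a question could be asked. The average spacing over 42 days is 42 / 8 = 5.25 days or 42 / 12 = 3.5 days.

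**The case against.** The strongest reply is that the PI already has a duty: "The PI will be responsible for monitoring and handling any potential problems that arise". It depends neither on the participant's attribution nor on the word injury, and nothing restricts it to volunteered complaints. Staff who are present while the cuff is used may notice problems. This stands, and it rules out a reading that is easy to reach, namely that harms are detected only when a participant reports them. The sentence assigns responsibility, however. It does not say what is asked, when, of whom or on what form, so it is not systematic collection.

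Second, the Injury section is addressed to the participant and is mostly about care and billing. It should not be read as the trial's collection rule or as excluding other collection. That also stands. The weight of the point rests on the silence of the session lists.

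Third, a reader might infer that reporting will differ between arms because the pressures differ, and that the experimental arm will look worse. The documents do not support this. They give different pressures and call the control condition a placebo inflation. They do not say what participants perceive or know, and each participant is assigned to only one condition. Neither the existence nor the direction of unequal reporting can be established.

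Fourth, the stated purpose is strength and hypertrophy, and no safety comparison is planned. This limits the statistical consequence to any tolerability statement that might be made later. It does not remove the safety reason for asking.

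Finally, it would be too strong to say that a participant who stops attending has no contact with the study. The protocol is silent on following up non-attenders, and the invitation to report an injury still applies to them.

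**Conclusion.** The point holds in a limited form. Apart from a general PI monitoring duty and self-report of a perceived research injury, no scheduled, standardised harms question appears at any session. Symptoms that participants do not put in that category therefore risk being missed.

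The size cannot be fixed from the documents. Under the assumed 20 per arm and 10% true risk, the chance that an arm records any case at all runs from 0.33 to 0.85 as the recorded share goes from 20% to 90%. The ratios of 2.5 and 0.4 under equal true risk show what unequal reporting could do if it occurred; they do not predict that it will. The planned strength and muscle-size analyses are not affected.

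The change is worth making before enrolment, because it is cheap and the missing data cannot be reconstructed afterwards.

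**What to change.** - At every existing training session and at Session 10, ask all participants in both arms the same short questions, with the same wording: pain, swelling, numbness, skin change, and any new medical event since the last visit.
- Record the answers by leg, regardless of presumed cause.
- Record the reason for each missed session and each withdrawal.
- Add one descriptive table of events by arm and by cuffed versus uncuffed leg. The left leg does the same exercise without a cuff, so it gives a within-person reference for ordinary training soreness.
- Reconcile the 8 labelled training sessions with the 12 implied by the stated frequency, since this sets the number of collection points.

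How a positive answer affects use of the cuff is a clinical matter for the sponsor and is not proposed here.

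The cost is one to two minutes per visit, so 9 to 18 minutes per participant over 9 visits or 13 to 26 minutes over 13, plus a brief contact with anyone who misses a session and one extra table. The downside is that more minor soreness will be recorded.

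### Four kinds of test on two outcomes, with no decisive comparison and no error control; the pre/post tests on the list do not test the added restriction

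*Combined protocol and SAP*

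**What the plan says.** The analysis plan is two sentences under Statistical Analyses. One names the software. The other says "Independent Samples t-tests, Paired samples t-test, repeated measures ANOVAs and two-way ANOVAs will all be employed to determine difference within and between groups". It then widens the scope to two further terms, trials and conditions, without defining either.

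Other sections bear on how that list would be used:

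- Study Purpose/Objective: the aim is to "investigate whether the addition of blood flow restriction to low load exercise" and so learn whether it "will result in changes in quadriceps hypertrophy or lower extremity strength". Neither outcome is called primary.
- Project Summary: "Both groups however will complete the exact same protocol throughout the entirety of the study". At the end of training, "muscle cross sectional area via ultrasound and 1RM will be re-tested and compared to the initial measurements".
- Methods and Procedures: both legs are measured at Session 1. Allocation follows: "After day 1 testing; randomly allocate subjects to either control group or experimental group". During training, "only right leg will have the occlusion cuff". The Session 10 re-test does not say which legs are measured.

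The documents state no alpha, sidedness, multiplicity rule, sample size or power.

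**The concern.** There are two separate problems.

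**Multiplicity.** At least three contrasts bear validly on the objective: the between-group difference in right-leg change (with two time points, the same test as group-by-time), the randomised comparison of right-leg values at re-test, and the group-by-leg-by-time contrast. Each can be run on two outcomes. The plan neither chooses among them nor controls error across them, so a positive finding could come from whichever test crossed 0.05.

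**Attribution.** The question is what restriction adds to the exercise, and both arms do the same exercise. A paired pre/post gain in the restriction arm mixes ordinary training gain with any cuff effect. A result that is significant in the restriction arm but not in control is not a comparison of the arms either. If such results were taken as evidence for restriction, training gain could be credited to the cuff. Adjusting alpha does not cure this, because the test addresses a different question.

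**Working it through.** The plan gives no figure to reproduce.

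**Inputs from the documents:** two randomised groups; two outcomes; two time points; baseline on both legs before allocation; cuff on the right leg only; four test types.

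**Assumed inputs:** two-sided 0.05 per test and no restriction effect. Base case: 10-20 per arm, pre/post correlation 0.8-0.9, between-leg correlation 0.85, between-outcome correlation 0.5. Wide range: 10 or 20 per arm, pre/post 0.6-0.95, leg 0.6-0.85, outcome 0.2-0.8.

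**Step 1. Simple reference.** For k independent tests the chance of at least one false positive is 1 - 0.95^k. For k = 2 this is 1 - 0.9025 = 9.75%; for k = 4 it is 1 - 0.8145 = 18.5%. The tests here are correlated, so the chance was simulated.

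**Step 2. Simulation of multiplicity.** Data were multivariate normal over outcome, leg and time, with no group effect: 20,000 trials per base-case setting and 10,000 per wide-range setting. Entries are the chance of at least one p < 0.05, with results favouring restriction in brackets.

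| Between-group tests run | Base case | Wide range |
|---|---|---|
| Right-leg change, 2 outcomes (2 tests) | 9% (4-5%) | 8-10% (4-5%) |
| Plus right-leg post-only (4 tests) | 17-18% (8-9%) | 14-19% (7-10%) |
| Plus group-by-leg-by-time (6 tests) | about 24% (12-13%) | not run |
| Illustrative 14 tests: also left leg and group main effects | 33-34% (18%) | 28-40% (15-22%) |
| Baseline-adjusted right leg with Holm | 4.5-4.9% (2.2-2.5%) | 4-5% (2-3%) |

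The nominal level is 5% (2.5%). The six-test row holds only the three contrasts that bear validly on the question, each on two outcomes.

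**Step 3. Simulation of attribution.** Base case, no restriction effect, same training gain in both arms. Gain is in SDs of the outcome. Entries are the chance for at least one of the two outcomes.

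| Common gain | Paired gain significant in restriction arm only | Paired gain significant in restriction arm |
|---|---|---|
| 0 | 4-5% | 4-5% |
| 0.2-0.3 SD | 21-40% | 24-92% |
| 0.5 SD | 0.5-38% | 78-100% |
| 0.7 SD | 0-19% | not tabulated |
| 1.0 SD | 0-1% | not tabulated |

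The first pattern fades at large gains because control then becomes significant too. The second grows with the gain. Both matter only if such a result is read as a restriction effect.

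**Step 4. Cost of Holm.** The smaller p-value must be below 0.025, so the critical value moves from 1.960 to 2.241. If the other outcome shows nothing:

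- Power 80% becomes Φ(1.960 + 0.842 - 2.241) = Φ(0.561) = 71%.
- Power 90% becomes Φ(1.960 + 1.282 - 2.241) = Φ(1.001) = 84%.
- Sample size ratio to restore 80%: ((2.241 + 0.842)/(1.960 + 0.842))² = (3.083/2.802)² = 1.21.

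**Step 5. Gain from baseline adjustment.** With pre/post correlation ρ, and the post-only variance set to 1, the change score has variance 2(1 - ρ) and the adjusted comparison 1 - ρ². At ρ = 0.8 these are 0.40 and 0.36. The adjusted variance is thus 0.36 of post-only and 0.36/0.40 = 0.90 of the change score.

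**The case against.** The strongest reply is that valid tests are already on the list. An independent t-test on change, or the group-by-time term of an ANOVA, answers the question, and the plan does promise between-group comparisons. That is true. The fault is that none of them is designated, and having several valid candidates with none chosen is what produces the multiplicity.

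The *or* in the objective could mean two parallel questions, and the title joins strength and hypertrophy with *and*. Under that reading joint control is partly a matter of judgement, and the two-test excess (9% against 5%) is modest. But a claim resting on either outcome still needs error control, and choosing among contrasts within one outcome remains open under both readings.

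The 14-test figure counts left-leg comparisons and group main effects that do not bear validly on the question, and it needs left-leg re-test data that Session 10 does not clearly promise. This stands: the figure is only illustrative, and about 24% for six tests is the better upper figure.

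The attribution problem depends on a reading the plan does not state. The Project Summary sentence on re-testing may describe only what is measured, and the paired test might pair legs rather than times. This also stands, so those percentages are conditional. A comparison of legs within the restriction arm would not compare with the control group either.

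Finally, group-by-time is valid too, and baseline adjustment improves on it only modestly at ρ = 0.8. Designating one contrast with an error rule is the essential step; baseline adjustment is the preferred choice, costing one degree of freedom and losing no precision in large samples.

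**Conclusion.** The concern holds. Followed as written, the plan allows a false-positive chance above 5% for a claim that restriction works: about 9% under the narrowest reading of the between-group tests on both outcomes, 17-18% with post-only tests, and about 24% across the three valid contrasts. About half of these errors would favour restriction. All of these rest on an assumed 0.05 per test and on assumed group sizes and correlations. The two-test figure stays at 8-10% and the four-test figure at 14-19% across the wide range. The attribution problem is certain in principle, but its size in this trial cannot be stated: it depends on the unknown common training gain and on how paired results would be read. This is a cheap improvement rather than a fatal flaw, since the design and the data to be collected support a sound analysis.

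**What to change.** Replace the list of tests with one confirmatory analysis:

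- **Contrast:** the between-group difference in the right (cuffed) leg at re-test, adjusted for its baseline value (ANCOVA). Baseline is measured before allocation, so it is a valid covariate.
- **Outcomes and error rule:** quadriceps cross-sectional area and 1RM, with Holm control at an overall two-sided 5%. Alternatively, name one as primary at 5% and the other as secondary.
- **Everything else:** report within-group paired changes, left-leg results and other ANOVA terms as descriptive or exploratory, and state that they will not support a claim that restriction works.
- **Re-test:** if left-leg results will be reported, state that both legs are re-tested.

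This takes a few lines of analysis text and no new data. The Holm option has the power cost worked out above: at worst, 80% falls to 71% and 90% to 84%, and about 21% more subjects would restore 80%. Actual power cannot be stated without a sample size. Baseline adjustment offsets part or all of this, depending on which test it replaces. Naming one primary outcome avoids the loss for that outcome.
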